2.1 Data analysis general information

The data will be analyzed by Novartis. Health economics input analysis will be provided by **Sector**. It is planned that the data from all centers that participate in this protocol will be used for analysis. Analysis datasets and statistical outputs will be produced using the most recent SAS[®] Version 9.4 (SAS Institute Inc., Cary, NC, USA), and stored in Novartis global programming & statistical environment (GPS).

The data from all centers will be pooled and summarized. Continuous data will be summarized by n, mean, standard deviation (SD), median, first and third quartiles, minimum and maximum. Categorical data will be presented by absolute and relative frequencies (n and %). Unless stated otherwise, two-sided p-values will be presented.

Decimal places

Decimal places will be as follows:

- p-value: 4 decimal places; if p-value is less than 0.0001, display <0.0001.
- standard error and standard deviation: data precision + 2 decimal places
- mean, quartile, percentile and median: data precision + 1 decimal place
- minimum and maximum: same as data precision
- percentages: 1 decimal place, 0% will be displayed as 0.0 and 100% will be displayed as 100.0.
- Odds ratios, risk ratios and hazard ratios will be displayed with 3 decimal places.
- Confidence interval (CI): data precision + 2 decimal place.

P-values will not be concatenated with "*" stars in case of significance.

2.1.1 General definitions

2.1.1.1 Study treatment: Study treatment refers to:

Secukinumab 300 mg (two s.c. injections of secukinumab 150 mg).

2.1.1.2 Study treatment start and end date:

Study treatment start date is defined as the first date when a non-zero dose of study drug is administered and recorded on the Dose Administration Record (DAR) CRF page. Similarly, study drug end date is defined as the last date when a non-zero dose of study drug is administered and recorded on the DAR CRF page.

2.1.1.3 Study day:

Study day will be calculated as (event date – study drug start date + 1 day) for events that occurred on or after study drug start date (e.g.visit, lab samples, AEs). For events prior to study drug start date (e.g., an adverse event occurred before the start of first dose), study day will be negative and calculated as (event date – study drug start date). Note that study drug start date is study day 1 and the day before study drug start date is study day -1 (i.e. no study day 0).

Due to the study drug dosing schedule, one month will be considered as 28 days. Time from events prior to the start of study drug, e.g., time since diagnosis, is calculated as the difference between the start date of study drug and the date of prior event.

Note that, the first dose day is Day 1, and the day before the first dose day is counted as Day - 1 (not Day 0).

2.1.1.4 Baseline and post baseline:

In general, a *baseline* value refers to measurement corresponding to week 0 assessment. A post-baseline value refers to a measurement taken after week 0 assessment.

Change from baseline will only be summarized for patients with both baseline and postbaseline unless stated otherwise, and it will be calculated as:

post-baseline value – baseline value

Correspondingly, percentage change will be calculated as:

100 * (post-baseline value – baseline value) / baseline value

For DLQI, In case baseline value is zero (0), percentage change will be calculated as (post-baseline value -0)*100 %.

2.1.1.5 Study periods:

The study has four periods: a screening period consisting of two visits (pre-screening and screening), an induction period of 4 weeks, a maintenance period of 20 weeks and an extension period of 48 weeks.

For analyses which will be done by phases (i.e., Core and Extension separately) the following rules will be applied to summarize the data.

For spontaneous data (CM, AE) as below:

• For the subjects who did not enter Extension Phase, all events/medications belongs to Core Phase

- · If event/medications start date is on or before visit date of E0, then APERIOD=Core Phase
- If event/medications start date is after visit date of E0, then APERIOD=Extension Phase.

For Planned data (i.e., Visit wise, all safety and efficacy) will be derived as below:

- · Visits before E0 will belong to Core Phase
- · Visits on or after E0 will belong to Extension Phase

Basically reporting will be done for visit assessment data in extension phase which is collected on or after ICF is signed for extension phase.

The above rules are irrespective of whether V12 visit date and E0 visit date are same or different.

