2.11 Patient-reported outcomes

Variables related to health-related quality of life (HR-QoL) are described below. All HR-QoL variables will be evaluated based on Safety set. Both prevalence and LOCF approach will be adopted.

Dermatology Life Quality Index

Seven scores will be derived from the DLQI: the total score of each of the six dimensions as well as the total score over all items. The higher the score, the more quality of life is impaired.

The percentage change from baseline will be derived for each of the seven scores. Summary statistics will be provided for absolute values as well as for the percentage change by visit.

Changes from baseline in DLQI at each time point will be analyzed by means of a paired ttest or Wilcoxon signed-rank test, based on data distribution.

In addition, summary statistics will be provided for the number of patients achieving DLQI 0 or 1 at each time point specifying absolute and relative frequency of patients with DLQI 0/1 response. Further, comparison between baseline and each time point for proportion of patients achieving DLQI 0 or 1 will be performed using McNemar's test.

Following details to the DLQI scoring: The scoring of each question is as follows

- Very much: scored 3
- A lot: scored 2
- A little: scored 1

- Not at all: scored 0
- Not relevant: scored 0
- Question unanswered: scored 0
- Question 7: "prevented work or studying": scored 3

The DLQI total score will be calculated by summing the score of each question resulting in a maximum of 30 and a minimum of 0. The highger the score, the more quality of life is impaired.

Meaning of DLQI scores:

- 0-1= no effect at all on patient's life
- 2-5= small effect on patient's life
- 6-10= moderate effect on patient's life
- 11-20= very large effect on patient's life
- 21-30= extremely large effect on patient's life

The DLQI will be analyzed under six headings as follows:

- Symptoms and feelings: questions 1 and 2, score maximum 6
- Daily activities: questions 3 and 4, score maximum 6
- Leisure: questions 5 and 6, score maximum 6
- Work and school: question 7, score maximum 3
- Personal relationships: question 8 and 9, score maximum 6
- Treatment: question 10, score maximum 3

Interpretation of incorrectly completed questinnaires:

There is very high success rate of accurate completion of the DLQI. However, sometimes patients do make mistakes.

- 1. If one question is left unanswered this is scored as 0.

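### The SAP's DLQI percent change for a zero baseline divides by an arbitrary 1 point, which pulls the mean percent change towards or above zero in a descriptive summary

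*SAP*

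**What the plan says.** SAP 2.1.1.4 defines change from baseline as post minus baseline, and percentage change as "100 * (post-baseline value – baseline value) / baseline value". It then adds an exception for one instrument, the DLQI: "In case baseline value is zero (0), percentage change will be calculated as" the post-baseline score, less zero, times 100%.

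SAP 2.11 applies percentage change to the DLQI total and all six dimensions: "The percentage change from baseline will be derived for each of the seven scores". It goes on: "Summary statistics will be provided for absolute values as well as for the percentage change by visit". SAP 2.1 fixes what is shown: "Continuous data will be summarized by n, mean, standard deviation (SD), median, first and third quartiles, minimum and maximum".

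The score ranges are short. SAP 2.11 lists, for example, "Work and school: question 7, score maximum 3" and "Symptoms and feelings: questions 1 and 2, score maximum 6". The total runs from 0 to 30. An answer of not relevant scores 0.

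Protocol 9.5.4 also plans percentage change for the seven scores but has no rule for a zero baseline. SAP Section 4 does not list the rule as a change to the protocol's analyses, and the SAP gives no reason for it.

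**The concern.** Percent change has no value when the baseline is 0. The rule supplies one by dividing by 1 point, so the result is raw points multiplied by 100. These values are then averaged with true percentages, which cannot fall below -100%. A zero-baseline patient can contribute only 0% or a positive number, so the distortion runs one way: the mean understates the percent improvement of the patients who had something to improve. The SD and the maximum can be inflated as well. DLQI is a stated secondary objective, and the rule feeds seven sets of by-visit tables.

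**Working it through.** The plan states no figure for DLQI percent change, so there is none to reproduce. The check applies the two SAP formulas to the score ranges and then works through a range of assumed cases.

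**1. What the rule assigns from a baseline of 0**

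- 0 to 0: 100 × 0 = 0%.
- 0 to 1: 100 × 1 = +100%. 0 to 3: +300%.
- Ceiling: 100 × 3 = +300% (one-item subscale), 100 × 6 = +600% (two-item subscale), 100 × 30 = +3000% (total).

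By the ordinary formula the same one-point rise is 100 × 1/2 = +50% from a baseline of 2, 100 × 1/10 = +10% from 10, and 100 × 1/15 = +6.7% from 15.

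**2. An invented set of ten patients**

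On one subscale, nine patients go from 3 to 0 (-100% each) and one goes from 0 to 1 (+100%).

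- Mean under the rule: (9 × (-100) + 100)/10 = -80%. With the zero-baseline patient left out it is -100%.
- If that patient goes from 0 to 3: (-900 + 300)/10 = -60%.
- Mean absolute change with 0 to 1: (9 × (-3) + 1)/10 = -2.6 points. No special rule is needed.

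**3. Can zero baselines occur?**

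Yes. Not-relevant answers score 0. Protocol 4.1 requires a DLQI of at least 10 only for patients with PASI above 5 but below 10, so even a zero total is possible for the others. A zero total needs every item to score 0. Apart from unanswered items, zeros are therefore at least as common in each subscale as in the total. How common they are is not stated.

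**4. Effect on the mean**

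Let f be the share with a zero baseline, m the mean percent change in the others, q the share of zero-baseline patients who rise, and r the points risen:

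mean = (1 - f) × m + f × q × 100 × r

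Assumptions, none of them from the documents: m = -80%; q from 0 to 20%; r of 1 or 2 points.

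| f | q = 0 | q = 20%, r = 2 |
|---|---|---|
| 1% | 0.99 × (-80) = -79.2% | -79.2 + 0.4 = -78.8% |
| 10% | 0.90 × (-80) = -72% | -72 + 4 = -68% |
| 30% | 0.70 × (-80) = -56% | -56 + 12 = -44% |

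A rise of 3 points in 10% of zero-baseline patients falls inside these ranges (-69% at f = 10%, -47% at f = 30%). A rise of 3 points in 20% of them would extend the upper ends to -72 + 6 = -66% and -56 + 18 = -38%.

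**5. Where the shift comes from**

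At f = 10%, entering zero-baseline patients at 0% moves the mean by 0.10 × 80 = 8 points, and the rises add 0 to 4. At f = 30% the figures are 24 and 0 to 12. Most of the shift comes from zeros entered as 0%, and less from inflated rises.

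**6. The median**

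If all the other patients sit at -80% and fewer than half have a zero baseline, the median stays at -80%. Once more than a quarter have a zero baseline, the third quartile moves to 0% or above.

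**The case against.** The best case for leaving the rule alone has four parts.

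- **No inference depends on it.** The endpoint in SAP Table 1.2-1 is change from baseline in DLQI. The paired t-test or Wilcoxon test is on changes, which SAP 2.1.1.4 defines as a difference. The McNemar comparison of DLQI 0/1 and the PASI 90 primary endpoint do not use percent change. This stands. A reader might infer that the secondary DLQI test is biased, but the documents do not support that.
- **The median and quartiles are reported beside the mean.** This also stands and limits the harm. It does not make the mean, SD or maximum correct.
- **The frequency of zeros is unknown.** A reader might infer from the short subscales that zero baselines will be frequent. The documents show only that they are possible. At 1% the effect is about one percentage point.
- **Entering 0 to 0 as no change is a defensible convention, and leaving these patients out has a cost.** They cannot improve, so excluding them removes only non-improvers, although the objective concerns all patients. The cost is real but small, because absolute values for all patients are already summarised. The convention also does not justify +100% per point for those who rise.

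Two further readings are tempting. One is that one-point rises counted as +100% cause most of the distortion; in the cases above they cause the smaller part. The other is that subscales carry the largest single values. The largest possible value is on the total (+3000%); the subscales are more exposed only because zeros are at least as common there.

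**Conclusion.** The point holds as a defect in one derivation rule with limited reach. The algebra is certain: the rule divides by an arbitrary 1 point, and its effect on the mean has a known direction whenever the other patients improve on average. The size is not certain. It depends on the share of zero baselines and on later scores in those patients, neither of which is in the documents. Under the stated assumptions it runs from about 1 percentage point at 1% zeros, through 8 to 12 points at 10%, to 24 to 36 points at 30%. The damage is confined to the mean, SD and maximum, and with many zeros the upper quartile, of the descriptive percent-change tables.

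**What to change.** In SAP 2.1.1.4, delete the zero-baseline sentence for DLQI and state that percent change is summarised only for patients with a baseline above 0 on the score concerned. In the DLQI tables of SAP 2.11, show for each score and visit the number of zero-baseline patients left out and their absolute scores. State that absolute change in all patients is the main DLQI summary for all seven scores.

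The cost is one deleted sentence, one added sentence and an extra row in the percent-change tables. No new data are needed and no test changes. The one downside is that the percent-change summary then describes only patients with a non-zero baseline, so the table title or footnote should say so.

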2.1.1.6 Visit windows

Visit windows will be used for the data that is summarized by visit. They are based on the study evaluation schedule and comprise a set of days around the nominal visit day. For any assessment, there are the protocol defined scheduled visits around which visit windows were created to cover the complete range of days within the study. The visit windows in this study are shown in the below Table 2.1, the days are counted since the first dose of study treatment. These visit windows apply to measurements taken at every visit. When visit windows are used, all visits will be re-aligned, i.e., they will be mapped into one of the visit windows. E.g., if the Week 4 visit of a patient is delayed and occurs on Day 46 instead of on Day 28, say, it will be re-aligned to visit window Week 8. If two visits fall into one window then the visit closest to target scheduled day will be analysed for that visit.

Visit	Week	Scheduled day	Visit Window
Screening (Visit1, Visit2)	-4	-28	-28 Days to Day -4
Baseline (Visit 3)	0	1	-3 day to Day 1
Visit 4	1	7	Day 2-10
Visit 5	2	14	Day 11-17
Visit 6	3	21	Day 18-24
Visit 7	4	28	Day 25-42
Visit 8	8	56	Day 43-70
Visit 9	12	84	Day 71-98
Visit 10	16	112	Day 99-126
Visit 11	20	140	Day 127-154
Visit 12	24	168	Day 155-210
E1	36	252	Day 211-294
E2	48	336	Day 295-378
E3	60	420	Day 379-462
E4	72	504	≥ 463 Day

Table 2.1	Assessment windows	for scheduled visits
-----------	--------------------	----------------------

Case 1) If V12 and E0 visit dates are same then:

Visit	Wk	Day	Window
V12	24	168	Day 155-210
E1	36	252	Day 211-294
E2	48	336	Day 295-378
E3	60	420	Day 379-462
E4	72	504	≥ 463 Day

Case 2) If	V12	and	E0	dates	are	different	then:

Visit	Wk	Day	Window
V12	24	168	Day 155-(A(E0)-1)
E0	24	A(E0)	A(E0) – (A(E0) +42)
E1	36	(A(E0) +43)+41	Day (A(E0) +43) – (A(E0) +43+83)
E2	48	(A(E0) +43+84)+41	Day (A(E0) +43+84) – (A(E0) +43+2*83)
E3	60	(A(E0) +43+2*83+1)+41	Day (A(E0) +43+2*83+1) – (A(E0) +43+3*83)
E4	72	(A(E0) +43+3*83+1)+41	> Day (A(E0) +43+3*83)

Where A(E0) date implies Actual Visit date of E0.

Note if A(E0) date = Day 168, which is the theoretical study day of V12, then both the table gives same windows.

If E0 is not assessed, then combine the window of E0 and E1 for E1 visit, i.e., E1 window will start from E0. Target day of E1 will remain same.

For parameters which are not collected at every visit (e.g. DLQI, HADS, **1999**), visit windows defined in Table 2.1 will be combined. For example, if a parameter is measured at Week 16 and Week 24 only, Week 16 visit window will extend from Day 2 to Day 126 (combining Week 1 to Week 16 visit windows), Week 24 will extend from Day 127 to Day 210 (combining Week 20 to Week 24 visit windows). Similarly, in extension phase, if a parameter is measured at E2 and E4 only, E2 window will extend from E0 to (A(E0) +43+2*83) (combining E0 to E2 visit windows).

For any assessments which are only in Core phase, and if any results are mapped to extension phase analyses visits, then such records will not be displayed at extension.

If more than one assessment falls into the interval, the rules defined in Section 2.1.1.7 below are applied.

The analysis visit will be used for listing of visit and period for safety data.

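### SAP 2.1.1.6: the Case 2 extension windows do not equal Table 2.1 at E0 = Day 168 as stated; 83-day multiples put the E2/E3 boundary 1 day early and the E3/E4 boundary 2 days early

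*SAP*

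**What the plan says.** SAP 2.1.1.6 gives two sets of extension windows. Table 2.1, repeated as Case 1 for patients whose V12 and E0 dates coincide, is fixed in study days: E1 211-294, E2 295-378, E3 379-462 and E4 from 463, with scheduled days 252, 336, 420 and 504.

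Case 2, for patients whose V12 and E0 dates differ, counts from E0: "Where A(E0) date implies Actual Visit date of E0". Its windows are as follows (each quote stops before the final bracket):

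- E1: "Day (A(E0) +43) – (A(E0) +43+83"
- E2: "Day (A(E0) +43+84) – (A(E0) +43+2*83"
- E3: "Day (A(E0) +43+2*83+1) – (A(E0) +43+3*83"
- E4: "> Day (A(E0) +43+3*83"

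Each target day is the window start plus 41. The SAP then gives a check of its own: if A(E0) is Day 168, the nominal day of V12, "then both the table gives same windows".

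For parameters measured in the extension only at E2 and E4, windows are combined and the same E2 limit returns: "E2 window will extend from E0 to (A(E0) +43+2*83".

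**The concern.** The note makes a testable statement, and the formulas fail it. The +83 in the E1 row is right, because an 84-day window ends 83 days after it starts. In the later rows that 83 is multiplied by 2 and 3 as if it were the step between visits, so each further window loses a day.

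These windows decide which record counts as week 48, 60 or 72. The target days decide which of two records in one window is analysed (SAP 2.1.1.6 and Table 2-2). PASI response by visit, and the part of the primary objective that runs to week 72, depend on them. A programmer who validates Case 2 against Table 2.1, as the note invites, will find a mismatch and no statement of which table governs.

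**Working it through.** **Inputs.** Windows, targets and the Day 168 note come from SAP 2.1.1.6. The extension schedule (weeks 24, 36, 48, 60, 72; ±7 days) comes from protocol Table 6-2 and the text above it. Write A for A(E0).

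**Step 1. Reduce the Case 2 formulas.**

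- E1: A+43 to A+43+83 = A+126; target A+43+41 = A+84
- E2: A+43+84 = A+127 to A+43+166 = A+209; target A+127+41 = A+168
- E3: A+43+166+1 = A+210 to A+43+249 = A+292; target A+210+41 = A+251
- E4: from A+43+249+1 = A+293; target A+293+41 = A+334

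**Step 2. Put in A = 168, the day for which equality is stated.**

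| Visit | Case 2 window (target) | Table 2.1 window (target) | Same? |
|---|---|---|---|
| E1 | 211-294 (252) | 211-294 (252) | yes |
| E2 | 295-377 (336) | 295-378 (336) | upper limit 1 day early |
| E3 | 378-460 (419) | 379-462 (420) | start and target 1 day early, end 2 days early |
| E4 | from 461 (502) | from 463 (504) | start and target 2 days early |

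At A = 168, Day 378 is therefore E2 in Table 2.1 but E3 in Case 2, and Days 461 and 462 are E3 in Table 2.1 but E4 in Case 2. From Day 211 on, no other day differs.

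**Step 3. Compare with the plan's own spacing.** Case 2 widths are 126-43+1 = 84 for E1, 209-127+1 = 83 for E2 and 292-210+1 = 83 for E3. The targets A+84, A+168, A+251 and A+334 are 84, 83 and 83 days apart. Visits 12 weeks apart need 12 × 7 = 84 throughout.

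**Step 4. Days moved in any Case 2 patient.** With 84-day steps, E2 would end at A+210, and E3 would run from A+211 to A+294. As written, A+210 goes to E3 instead of E2, and A+293 and A+294 go to E4 instead of E3. That is three days per Case 2 patient, whatever A is.

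**Step 5. Can scheduled visits reach them?** At A = 168, visits within ±7 days fall on 329-343 (E2), 413-427 (E3) and 497-511 (E4). The nearest affected day is 461, which is 461-427 = 34 days from a scheduled visit. If E0 is itself within ±7 days of Day 168, the boundaries move by at most 7 days, which leaves at least 27. Only off-schedule records are exposed.

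**Step 6. Near-ties.** A target 2 days early can change the record chosen. With records on Days 499 and 507 and A = 168, target 504 selects Day 507 (distance 3 against 5), while target 502 selects Day 499 (3 against 5).

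**Step 7. DLQI and HADS.** Both are collected in the extension only at weeks 48 and 72. The combined E2 window ends at A+209, so a questionnaire on A+210 falls to week 72, if E3 and E4 are combined by the same rule, instead of week 48. Only this one boundary day is affected.

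**The case against.** The best defence is that Case 2 works as written. The windows A+43 to A+126, A+127 to A+209, A+210 to A+292 and above A+292 are contiguous and do not overlap, so every record maps to exactly one visit. On this view the false sentence is only an explanatory note, and deleting it would remove the contradiction. The contiguity stands. Deleting the note would still leave E2 and E3 a day narrower than E1, and targets that drift from the 12-week schedule. The note is also the clearest evidence that 84-day steps were meant.

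A reader might infer more: that because of the 83, one study day generally belongs to different visits depending on whether V12 and E0 share a date. The documents do not support that. Case 2 is anchored on the actual E0 date and Case 1 is fixed, so the two differ by design whenever A is not 168, and the correction does not change this. Counting V12 and E0 as one visit, the days that map differently from Table 2.1 are:

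| A(E0) | As written | With 84-day steps |
|---|---|---|
| 165 | 15 | 12 |
| 168 | 3 | 0 |
| 169 | 3 | 4 |
| 170 | 5 | 8 |
| 175 | 25 | 28 |

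For A after 168 in this table, the correction slightly increases the count. Nor do Days 378, 461 and 462 serve as general examples. At A = 169 the Case 2 E2 window is 296-378, so Day 378 is E2 in both cases. At A = 170 E3 is 380-462, so Days 461 and 462 are E3 in both.

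**Conclusion.** The stated equality is wrong from the E2 upper limit onward. In Case 2 patients the E2/E3 boundary and the E3 target are 1 day early, and the E3/E4 boundary and the E4 target 2 days early, relative to 84-day spacing from E0. This is arithmetic on the SAP's own formulas. Its only assumption is that 84-day spacing was meant, which the note, Table 2.1, the E1 row and the visit schedule all indicate.

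The consequence is very small. It needs an off-schedule record on one of three days, or two records nearly equidistant from an E3 or E4 target, in a Case 2 patient. The documents give neither the number of Case 2 patients nor the number of off-schedule records. For scale only, assume 30 to 60 off-schedule records spread evenly over the 48 × 7 = 336 extension days: 30 × 3/336 = 0.27 to 60 × 3/336 = 0.54 records would move. That is an upper figure, because it treats every such record as coming from a Case 2 patient. The Week 16 window (Days 99-126), and so the comparison against the 12% margin, is unaffected. This is a minor correction, worth making because the rule is operational and fails the check printed beside it.

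**What to change.** In the Case 2 table, set the upper limits to A(E0)+43+2*84-1 for E2 and A(E0)+43+3*84-1 for E3, and carry them into the E3 and E4 starts and targets:

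- E2: A+127 to A+210 (target A+168, unchanged)
- E3: A+211 to A+294, target A+252
- E4: from A+295, target A+336

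End the combined E2 window, for parameters measured only at E2 and E4, at A(E0)+210.

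Check at A = 168: E2 295-378 (336), E3 379-462 (420), E4 from 463 (504). E1 stays 211-294 (252). This is Table 2.1 exactly, so the note becomes true and can stay.

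Do not simply replace every 83 by 84. At A = 168 that gives E1 211-295 and E2 295-379, which overlap on Day 295; the +83 in the E1 row is already correct.

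The cost is one SAP table, one sentence and the matching line of code. No data collection changes.
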